Study Title: Decisional Capacity and Informed Consent in Fragile X Syndrome

NCT number: 02465931

Most recent IRB approval date: June 11, 2018

Date of the document: November 8, 2018

Trial Design

We will use a two-arm, parallel design randomized control trial (RCT) with a 1:1 allocation ratio.

Participants will be randomized into either the control or experimental group. Both groups will be exposed to the same informed consent content but delivered via different channels: a digital informed consent application (experimental) or paper informed consent/usual practice (control). The content of both versions of the informed consent describes the requirements for participating in a hypothetical clinical trial for a fake prescription drug for FXS. Both versions include IRB-required information (e.g., study procedures, study duration, compensation). The digital informed consent application does not meet all of the regulated technical requirements for electronic informed consent (i.e., the signature component).

Table 1. Overview of the study design, with details regarding how the variables differ across conditions.

Component	Control	Experimental
Delivery of information	Paper informed consent form paired with verbal overview of key points	Paper informed consent form paired with tablet-based tool which contains visual and audio components
Language	Complex (paper) and simplified (verbal overview)	Complex (paper) and simplified (tablet-based tool)
Exposure to information	Paper informed consent form will be sent to participant and family before data collection visit. They will be able to review as many times as they wish before visit. During visits, simplified overview of informed consent form will be provided in person just once .	Paper informed consent form will be sent to participant and family before data collection visit. They will be able to review as many times as they wish before visit. During visit, the participant can go through the tablet-based tool up to 3 times.
MacCAT questions	All questions will be asked after the disclosure information has been presented. Questions will have the same wording as experimental condition. Procedures will mimic MacCAT/flipchart (incorrect or partial credit will be given opportunity to answer question again after disclosure information is repeated).	All questions will be embedded within the vignettes/presentation of disclosure information. Use simplified wording for questions-similar to flipchart. Procedures will mimic MacCAT/flipchart (incorrect or partial credit will be given opportunity to answer question again after disclosure information is repeated).

	Multiple choice options rather than open-ended. Paper and pencil data collection	Multiple choice options rather than open-ended. Response data stored within tool and exported to dataset for analysis.
--	---	---

Participants

Up to 50 pairs of adolescents or adults (aged 14 or older) with FXS, a subset of 250 individuals who completed a battery of neurocognitive assessments (including IQ, reading abilities, autism and anxiety co-morbidities) between 2013-2016, will participate in the study.

Recruitment

Three primary methods will be used for recruitment: (1) recontacting the families who have participated in prior longitudinal assessment studies conducted by the research team; (2) recruiting through the FX research registry maintained by the University of North Carolina at Chapel Hill; and (3) announcing the research on the National Fragile X Foundation Web site. We have been highly successful in recruiting FX study participants, including a large national survey of over 1,000 families [45] so anticipate few problems in recruiting an adequate sample.

Inclusion / Exclusion

Eligibility will be determined by a person's scores on an initial assessment which included a standardized IQ and autism measure. Participants will be excluded if he or she (1) receives a score of 30 or less on the IQ measure; (2) receives a score between 31-40 on the IQ measure and has a diagnosis of autism with severe autism symptoms as noted on a standardized autism measure; or (3) is determined to have other behavioral challenges that would preclude their inclusion (e.g. mutism, severe aggression). These exclusion criteria cut offs were established to ensure a minimal level of comprehension and adaptive behavior for the study; IQs of 35 or below are indicative of severe intellectual disability.

Intervention

Control group. Participants randomized to the control group will be exposed to a paper consent form that covers the same informed consent information presented in the tablet-based application and mimics informed consent forms used for real clinical trials. The complex language that is typically used in current standard practice (i.e., *participation vs. take part*) will be retained in the paper version. The control group will be designed to mimic typical informed consent procedures, i.e., the verbal transmission of study information from a clinician to the individual and caregivers. To standardize this practice, we will develop a script that is verbally reviewed with control group participants including a simplified overview of the key information in the paper consent form.

Experimental group: Participants randomized to the experimental group will receive the paper consent form (the same form the control group participants received) and will also be exposed to the tablet-based application. Given that the digital application does not meet the requirements of electronic consent, the paper consent form will still be needed for documenting that informed consent was obtained.

Randomization

We will employ a stratified, block randomization method to assign participants to the control or experimental group. Two stratification variables will be used: Verbal IQ score (3 levels) and age (2 levels). Age was selected as a randomizing variable because children and adolescents under 18 are not able to provide informed consent, only assent, as their parents are their legal guardians. Verbal IQ was selected as a second variable because we had a small sample size and wanted to control for any possible effects on the outcome variables. However, we could have also chosen to account for any possible group differences based on IQ through statistical analyses. Given that enrollment for the RCT will be

done on a rolling basis, a 10 block, 2 group design will be used. Thus, we will randomize 10 participants at a time into either the control or experimental group. We will utilize a random number generator (www.randomizer.com) to make the assignments.

Blinding

Due to the nature of the study, participants and data collectors were not blinded to group assignment.

Study Setting and Data Collection Procedures

Each study session will occur in the individual's home and will be videotaped to allow subsequent coding of individual engagement in the decisional process. Approximately 10 days prior to the visit, the participant and/or their primary caregiver will be sent the standard paper consent form for a hypothetical clinical trial. All participants, including parents and caregivers, will be informed that the clinical trial is hypothetical. Participants will be asked to review the consent form as they would any research consent form.

On the day of the visit, parents and individuals with FXS who are their own legal guardian will be asked to complete a 5- to 10-minute pre-test to assess their/their child's belief and attitudes about participating in clinical trials. Pre-test items included questions such as the participant's possible reasons for participating in clinical trials, the likelihood of participating, and who they think should make the decision about enrolling in a trial (full list of domains in Study Outcomes section below). Participants will then complete either the experimental or control group informed consent procedure. Both the control and experimental groups will be asked the modified MacCAT examination items throughout the informed consent process to assess decisional capacity. The questions are identical for each group. After the informed consent procedure, all participants will again be asked to complete the post-test questions about their beliefs and attitudes about clinical trials

Study Outcomes

The following measures will be collected as part of the study protocol:

- Time spent with decision aid or in discussion with research assistant
- Perceptions about reasons to participate in trials (e.g., altruism; pre- and post-test item)
- Likelihood of enrolling in a clinical trial (pre- and post-test item)
- Preferred level of involvement in the decision (pre- and post-test item)
- Self-efficacy related to decision-making ability (pre- and post-test item)
- Level of engagement in the decision-making process (pre- and post-test item)
- Satisfaction with the decision (post-test only)
- Perceived value of the educational information provided (post-test only)
- Session analytics, including time on page and session duration

Participant Timeline

Pre-test measures, the intervention or control condition, and post-test measures will all be conducted on the same day during an approximately 1-hour study session. The pre-and post-test measures will take approximately 15 minutes to complete and the control and intervention condition will last approximately 30 minutes. No additional follow-up is planned.

Statistical Methods

In the analyses, we will examine the effect of the app on decisional capacity, controlling for sociodemographic characteristics and severity of delay. We will first conduct bivariate analyses comparing decisional capacity, decision making preferences, and likelihood of trial participation across the two study groups (tablet vs. standard procedure), using chi-square tests for categorical outcomes

and t-tests for continuous outcomes. In addition, we will conduct multiple regression models to compare study outcomes by study group after controlling for demographics and severity of developmental delay. Linear regression models will be conducted for continuous outcomes (e.g., decisional capacity scores, preferences) and logistic regression models for categorical outcomes (e.g., likelihood of participating in a hypothetical trial). Within these models, we will test for interactions between study group and demographic characteristics to identify differential impact of the intervention on particular subgroups. For example, testing an interaction between study group and severity of delay would allow us to determine if the tablet-based intervention is more or less successful among more impaired participants.

[figure not shown]
Power Analyses

To determine the recommended sample size, we have conducted a power analysis using a between-subjects design (i.e., participants are randomized to control or experimental group). See Figure 1 below. With a sample size of 70 (35 participants per group), we will have 90% power to detect an effect size of .75.

Figure 1. FXS Power Analysis

t tests – Means: Difference between two independent means (two groups)

Tail(s) = One, α err prob = 0.05, Allocation ratio $N2/N1 = 1$

Ethics and Confidentiality

This research protocol was reviewed and approved by two Independent Review Boards from the University of North Carolina Office of Human Research Ethics (IRB Number: 13-1128) and RTI International Office of Research Protection (0281200.276). This study has been registered with ClinicalTrials.gov (NCT02465931).

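### Baseline reading ability is on file and plausibly prognostic for the capacity score, but the plan does not name it as a covariate; naming it is a cheap, optional gain in precision

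*Combined protocol and SAP*

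**What the plan says.** Statistical Methods gives the adjustment set twice. The opening sentence speaks of "controlling for sociodemographic characteristics and severity of delay". The later sentence on regression models says that they will "compare study outcomes by study group after controlling for demographics and severity of developmental delay". Neither names reading, and neither says how severity is measured.

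The Participants section describes the sample as a subset of 250 individuals who completed "a battery of neurocognitive assessments (including IQ, reading abilities, autism and anxiety co-morbidities) between 2013-2016". Those scores predate randomisation.

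Table 1 (Trial Design) gives the control arm as "Paper informed consent form paired with verbal overview of key points" and the experimental arm as "Paper informed consent form paired with tablet-based tool which contains visual and audio components". The Intervention section confirms that the form is the same in both arms and keeps the complex wording of usual practice. Study Setting and Data Collection Procedures has it sent to the participant, the primary caregiver or both about 10 days before the visit.

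Randomization stratifies on Verbal IQ (3 levels) and age (2 levels), and not on reading.

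**The concern.** A baseline score that predicts the outcome narrows the interval for the treatment effect when it enters a linear model, and it corrects for chance imbalance between arms. Reading is a reasonable candidate here: every participant's material includes a text in difficult language, and the capacity items test the content of that text. The sponsor already accepts the principle, since Randomization explains the choice of Verbal IQ by the small sample and the wish to control its effect on outcomes, and mentions statistical adjustment as an alternative.

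What is at stake is a somewhat wider interval than necessary in a trial of at most 50 pairs. The validity of the comparison is not at stake.

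**Working it through.** **Inputs from the documents.** Effect size d = 0.75, one-sided alpha 0.05, two-group t-test and 35 per group (Power Analyses); ceiling of 50 pairs (Participants) and 1:1 allocation (Trial Design), hence 25 per arm.

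**Input not in the documents.** R², the share of the outcome variance left after the other covariates that reading explains. Assumed values are 1%, 5%, 10% and 20%.

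**The plan's own figure.** Power is the probability that a noncentral t with 2n − 2 degrees of freedom and noncentrality d·√(n/2) exceeds the one-sided 5% critical value. With n = 35, the noncentrality is 0.75 × √17.5 = 3.137 and power is 92.8%. The plan states 90%, so its figure does not reproduce exactly but errs on the cautious side; 90% needs 32 per group. With n = 25, the noncentrality is 0.75 × √12.5 = 2.652 and power is 83.4%.

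**Adding reading.** The residual variance is multiplied by (1 − R²), so d becomes 0.75/√(1 − R²), and one error degree of freedom is lost (2n − 3). The standard error falls by 1 − √(1 − R²). Here d = 0.75 is taken on the residual SD before reading enters, and degrees of freedom used by the other covariates are ignored.

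| Assumed R² | SE reduction | d after adjustment | Power, 25 per arm | Power, 35 per arm |
|---|---|---|---|---|
| none | – | 0.750 | 83.4% | 92.8% |
| 1% | 0.5% | 0.754 | 83.7% | 93.0% |
| 5% | 2.5% | 0.769 | 85.0% | 93.8% |
| 10% | 5.1% | 0.791 | 86.6% | 94.8% |
| 20% | 10.6% | 0.839 | 89.9% | 96.6% |

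All entries are one-sided, as the plan states. With a two-sided test at 25 per arm, power would go from 73.8% to 74.2%, 76.0%, 78.2% or 82.7%.

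**Cost of the covariate if it explains nothing.** Moving from 48 to 47 degrees of freedom at 25 per arm costs 0.02 percentage point of power one-sided and 0.04 two-sided.

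**How large could R² be?** It is the squared partial correlation of reading with the outcome given severity: partial r = (r_RY − r_SY·r_RS)/√[(1 − r_SY²)(1 − r_RS²)], where R is reading, S severity and Y the capacity score. As an illustration, let reading and severity each correlate 0.5 with the outcome.

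- If they correlate 0.5 with each other: partial r = (0.5 − 0.25)/0.75 = 0.33, so R² is about 11%.
- If they correlate 0.8 with each other: partial r = (0.5 − 0.40)/√(0.75 × 0.36) = 0.19, so R² is about 4%.

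With outcome correlations between 0.4 and 0.6 and a reading–severity correlation between 0.5 and 0.8, R² runs from about 0% to 26%. These correlations are all assumed.

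**The case against.** Several stronger readings are tempting, and the documents do not support them.

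- **A reader might infer that the trial compares paper with audio, so that reading bears directly on the contrast between arms.** It does not. Both arms get the same paper form and then a simplified presentation that need not be read: spoken in the control arm, audio-visual on the tablet. The arms differ in channel, visuals, number of exposures (once against up to 3 times) and placement of the questions. The form may also be read by the caregiver. The case for reading rests on the shared paper form, and that makes it plausible as a predictor without proving it.
- **A reader might infer that available precision is definitely lost.** That is not shown. Severity of delay is undefined, may be IQ-based and may overlap heavily with reading. It cannot even be excluded that a battery score such as reading feeds into it. The gain could be close to nil.
- **A reader might infer bias or serious imbalance.** Randomisation removes bias in expectation from the linear comparison, and stratifying on Verbal IQ limits imbalance in reading to the extent that the two are related.

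The scores also have limits. They date from 2013-2016, and recruitment through a registry and a web-site announcement sits uneasily with every participant having been in the assessed group, so some scores may be missing. Finally, adjusting for the stratifiers is the more obvious first step, and reading has no proven claim over the other battery scores.

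All of this stands, and it reduces the size and urgency of the point. It does not remove it: a pre-randomisation, plausibly prognostic score is available for the drawn sample, it is not named, and using it costs almost nothing even when it adds nothing.

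**Conclusion.** The point holds as a minor, optional improvement in precision. At the 50-pair ceiling, on the plan's one-sided test, the gain in power runs from 0.3 point (83.7 − 83.4) if reading adds 1% of variance to 6.5 points (89.9 − 83.4) if it adds 20%. At 35 per arm the same range is 0.2 to 3.8 points. These figures rest on the assumed R² range, on d = 0.75 relative to the residual SD before reading is added, on a linear relation between reading and the capacity score, and on scores being available for nearly everyone. Old or missing scores would shrink the gain. The accompanying gap, that severity of delay has no stated measure, needs closing in any case, because the value of reading cannot be judged without it.

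**What to change.** Before analysis, state the covariates of the linear model for the capacity score: study group, the severity measure (defined), the stratifiers Verbal IQ and age, the chosen demographics, and the baseline reading score as one continuous term. Add a rule for missing reading scores, such as the overall mean across both arms or a missing-score indicator, fixed without reference to outcomes. If the sponsor prefers to leave reading out, one sentence giving the reason is enough.

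The cost is a line or two of wording and no new data collection. The statistical price is one degree of freedom for reading, plus one more if an indicator is used.

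### Items collected before and after the session: the plan does not use the pre-test response or say whether the outcome is post-test or change, which costs some precision on continuous items (minor)

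*Combined protocol and SAP*

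**What the plan says.** Study Outcomes marks five measures as collected twice: reasons for taking part, likelihood of enrolling, preferred involvement, self-efficacy and engagement. Two of the entries read "Preferred level of involvement in the decision (pre- and post-test item") and "Self-efficacy related to decision-making ability (pre- and post-test item").

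Statistical Methods starts with bivariate tests "comparing decisional capacity, decision making preferences, and likelihood of trial participation across the two study groups", using chi-square for categorical and t-tests for continuous outcomes. It then states that "we will conduct multiple regression models to compare study outcomes by study group after controlling for demographics and severity of developmental delay", and adds interactions with study group. On scale it says "Linear regression models will be conducted for continuous outcomes (e.g., decisional capacity scores, preferences"). For outcomes on the other kind of scale, the same sentence plans "logistic regression models for categorical outcomes (e.g., likelihood of participating in a hypothetical trial"). So among the twice-collected items, preferences are named as continuous and likelihood of participating as categorical. The scales of the other three are not stated.

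On who answers, Study Setting and Data Collection Procedures says that "parents and individuals with FXS who are their own legal guardian will be asked to complete a 5- to 10-minute pre-test", and later that "all participants will again be asked to complete the post-test questions about their beliefs and attitudes about clinical trials". The Blinding section says that neither participants nor data collectors were blinded.

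**The concern.** A pre-test response from the same person on the same item, taken about an hour before the post-test, may predict the post-test response better than demographic variables or severity of delay. If it is left out, a chance difference between arms at pre-test carries into the post-test comparison, and the interval is wider than the data require. The sample is small, and the Randomization section gives that as its reason for controlling for Verbal IQ.

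The second gap is the form of the outcome. Collecting an item twice invites a change-score analysis, and the plan neither adopts nor excludes one. The two forms differ in precision, and an undefined outcome leaves room to choose after the results are seen.

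**Working it through.** **The plan's own figure.** Power Analyses gives 90% power for 35 per group, effect size 0.75, one-sided alpha 0.05, two-sample t-test. The noncentrality is 0.75 × √(35/2) = 3.14 on 68 df, and exact power is 92.8%. The stated 90% is therefore slightly conservative for its own inputs. It uses no covariate and names no outcome, so it does not bear on the pre-test question.

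**Inputs.**
- Arm size: 35 (Power Analyses), or 25 if the cap of 50 pairs in Participants is split 1:1 and each pair supplies one respondent of each type (my reading).
- Pre/post correlation ρ: not in the documents; assumed 0.3, 0.5, 0.7.
- Four covariates standing for demographics and severity, explaining 20% of variance at pre-test and at post-test: assumed.
- Item SD set to 1.

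**Residual variance.** The planned regression leaves 0.8. If the covariates act equally on both measurements, they account for 0.2 of ρ, and the pre/post correlation that remains is r = (ρ − 0.2)/0.8.

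| ρ | r | 0.8(1 − r²) | SD factor √(1 − r²) |
|---|---|---|---|
| 0.3 | 0.125 | 0.7875 | 0.99 |
| 0.5 | 0.375 | 0.6875 | 0.93 |
| 0.7 | 0.625 | 0.4875 | 0.78 |

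**Interval width.** With k covariates and n per arm, the width is approximately 2 × t × √[(2/n) × residual variance × (1 + k/(2n − k − 3))], on 2n − 2 − k df.
- n = 25, planned (k = 4): 2 × 2.015 × √(0.08 × 0.8 × 1.093) = 1.07.
- n = 25, with pre-test (k = 5): 2 × 2.017 × √(0.08 × 0.8 × 1.119) = 1.079, times the SD factor, which gives 1.07, 1.00 and 0.84.

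Simulation gives mean widths about half a percent smaller, because the formula ignores the slight downward bias of an estimated SD:

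| per arm | planned | ρ = 0.3 | ρ = 0.5 | ρ = 0.7 |
|---|---|---|---|---|
| 25 | 1.06 | 1.06 | 0.99 | 0.84 |
| 35 | 0.88 | 0.88 | 0.82 | 0.69 |

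For illustration at effect size 0.75, one-sided 0.05: simulated power at 25 per arm goes from 0.87–0.88 to 0.87, 0.91 and 0.97; at 35 per arm, from 0.96 to 0.96, 0.97 and 0.995.

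**The result at ρ = 0.3 depends on the equal-effects assumption.** If the covariates act on pre-test and post-test through unrelated combinations, they account for none of ρ, so r = 0.3/0.8 = 0.375. The width at 25 per arm is then about 1.00 rather than 1.06.

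**If change scores were meant.** The variance of a change is 2(1 − ρ).
- Against the unadjusted post-test t-test (variance 1), change is less precise when 2(1 − ρ) > 1, that is ρ < 0.5.
- Against the planned post-test regression (0.8), covariates that act equally cancel out of the change, so change is less precise when 2(1 − ρ) > 0.8, that is ρ < 0.6.
- Against the pre-test-adjusted model, the variances are 1.4 v 0.7875, 1.0 v 0.6875 and 0.6 v 0.4875. The ratios are 1.78, 1.45 and 1.23, so the loss is largest at low ρ. Simulated power at 25 per arm agrees: the change-score t-test gives 0.709 against 0.874 adjusted at ρ = 0.3, and 0.957 against 0.969 at ρ = 0.7.

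**Validity.** In a simpler simulation without the other covariates, both the post-test-only and the pre-test-adjusted comparison recovered a true difference of 0.50, and one-sided error stayed between 4.9% and 5.2%.

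**Effect of knowing the arm.** Suppose knowing the assignment raised pre-test answers in the tablet arm by 0.2 SD (assumed). With pre-test slope (ρ − 0.2)/0.8, the adjusted effect moves by 0.2 times that slope: 0.025, 0.075 and 0.125 SD toward zero.

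**The case against.** The case for leaving the plan alone is fair. Its stated aim is the app's effect on decisional capacity, which this point does not touch. Only one twice-collected item is documented as continuous. The correlation and the covariate strength are assumed, and 0.75 is not tied to any attitude item. At 35 per arm the power gain is at most about 4 points. The word again in the post-test sentence may simply mean that the post-test respondents are those who took the pre-test. All of this stands, and it is why the point is minor. It does not remove the unused pre-test or the undefined outcome.

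A reader might infer more than the documents support:
- That the planned comparisons are biased or have wrong error rates. Randomisation protects them.
- That all five items lose precision in the way shown. Likelihood of participating is treated as categorical and three scales are unstated, so the figures apply only to items scored as continuous.
- That precision is lost only at moderate or high correlation. That is so for post-test outcomes under equal covariate effects, and it reverses if change scores were intended.
- That respondents know their arm before the pre-test. The trial is unblinded, but no section says when the assignment is disclosed.

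**Conclusion.** The point holds as a minor one about precision and outcome definition. For twice-collected items scored as continuous, with preferred involvement the documented case, the plan leaves the pre-test response unused and does not define the outcome. On the stated assumptions, using the pre-test shortens the 95% interval by between nothing (ρ = 0.3) and about a fifth (ρ = 0.7: 1.06 to 0.84 SD at 25 per arm, 0.88 to 0.69 SD at 35). The low-correlation result is less pessimistic if the covariates act differently on the two measurements. Under a change-score reading the pattern reverses, and below ρ of about 0.6 change scores are also less precise than the planned post-test regression.

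**What to change.** In Statistical Methods:

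1. State which twice-collected items are scored as continuous, and define their outcome as the post-test response.
2. For those items, add the same respondent's pre-test response as a covariate in the planned linear regression, wherever that respondent type completes a pre-test. Model parents and individuals with FXS separately.
3. State that the pre-test is completed before the respondent learns the assigned arm. If that cannot be assured, keep the planned model as the main analysis and report the pre-test-adjusted model as a sensitivity analysis.

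The decisional capacity analysis stays as planned.

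The cost is one model term and a few sentences, with no new data. If the correlation is low, the gain is little or nothing.

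### Likelihood of trial participation is planned for a chi-square test that ignores order and a logistic model of unstated form, which loses power if the item has three or more response levels

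*Combined protocol and SAP*

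**What the plan says.** Statistical Methods opens with bivariate analyses "comparing decisional capacity, decision making preferences, and likelihood of trial participation across the two study groups", using chi-square tests for categorical outcomes and t-tests for continuous ones. Regression follows, adjusted for demographics and severity of delay. The likelihood item is put in the categorical class: "logistic regression models for categorical outcomes (e.g., likelihood of participating in a hypothetical trial". Preferences are put in the other class: "Linear regression models will be conducted for continuous outcomes (e.g., decisional capacity scores, preferences". No rank, trend or ordinal method is named.

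Study Outcomes lists the two items as "Likelihood of enrolling in a clinical trial (pre- and post-test item" and "Preferred level of involvement in the decision (pre- and post-test item". Study Setting and Data Collection Procedures gives examples of pre-test content, including "the likelihood of participating, and who they think should make the decision about enrolling in a trial", and refers the reader to Study Outcomes for the full list of domains. None of these sections gives response options, number of levels, scoring or a cut-point for the likelihood item, or says whether the logistic model is binary, ordinal or multinomial.

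**The concern.** A question about how likely someone is to join a trial is often answered on a graded scale. If it has three or more levels, the levels have an order, and a Pearson chi-square gives the same result however the columns are shuffled. It spreads its sensitivity over every pattern of difference between arms, when the pattern of interest is a shift up or down.

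The regression step is open in another way. If the model is binary, someone must choose where to cut the scale, and the plan does not say where. Power depends heavily on that choice. Participants and data collectors know the assignment (Blinding section), which is a further reason to fix the coding before data are seen.

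At stake is power, and freedom from a post hoc cut-point, on one of the three outcomes named for the between-group comparison in a small trial.

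**Working it through.** **Inputs from the documents.** Power Analyses: 35 per group, standardised difference 0.75, one-tailed 0.05, 1:1 allocation. Participants: up to 50 pairs, so 50/2 = 25 per arm. The gap between 70 and 50 is a separate matter; both sizes are used here only to bracket the result.

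**The plan's own power figure.** The plan states: "With a sample size of 70 (35 participants per group), we will have 90% power to detect an effect size of .75". For a two-sample t-test the noncentrality is 0.75 × √(35/2) = 3.14 on 68 df. One-tailed power is then 92.8%, somewhat above the stated 90%; two-sided it is 87.1%. At 25 per arm the noncentrality is 0.75 × √(25/2) = 2.65, giving 83.4% one-tailed and 73.8% two-sided. This calculation is for a difference in means and is not tied to the likelihood item. The 0.75 is borrowed below only as a yardstick.

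**Tests compared, all at two-sided 0.05.**
- Pearson chi-square on the 2 × K table: X² = Σ(O − E)²/E on K − 1 df.
- The same test after collapsing the scale to two levels.
- Wilcoxon/Mann-Whitney with tie correction: variance of the rank sum = (n₁n₂/12) × [(N + 1) − Σ(t³ − t)/(N(N − 1))], where t is the number of participants at each level. This is the score test for group in the proportional-odds model.

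**Simulation 1: normal latent variable shifted by 0.75 SD.** The number of levels is assumed to be 3 to 5, because the documents give none. Levels are evenly filled or, for five levels, also filled 5/10/20/30/35%.

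| Per arm | Chi-square | Mid-scale split | Rank test |
|---|---|---|---|
| 35 | 54-67% | 59-69% | 77-82% |
| 25 | 35-52% | 47-61% | 62-68% |

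**Simulation 2: proportional odds, 40,000 trials per scenario.** A 0.75 SD shift corresponds to an odds ratio of about exp(0.75 × π/√3) = 3.9, so OR 4 is the nearest scenario run.

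| Per arm, levels | Rank test | Chi-square | Best cut | Worst cut |
|---|---|---|---|---|
| 35, 3 even | 85.1% | 76.7% | 79.3% | 62.0% |
| 35, 5 even | 88.6% | 70.2% | 79.3% | 45.2% |
| 25, 3 even | 71.2% | 61.0% | 71.1% | 50.4% |
| 25, 5 even | 76.1% | 52.5% | 70.0% | 33.4% |

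Relative loss with the chi-square at 35 per arm is (85.1 − 76.7)/85.1 = 10% with three levels and (88.6 − 70.2)/88.6 = 21% with five. At 25 per arm with five levels it is (76.1 − 52.5)/76.1 = 31%. Over 3 to 7 levels, OR 2 to 5 and both sample sizes, the chi-square loses 6% to 57% of the rank test's power and the best binary cut loses 0% to 24%.

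**Two-level item.** Here the squared Wilcoxon statistic equals X² × (N − 1)/N, that is 69/70 = 0.99 of X² at N = 70 and 49/50 = 0.98 at N = 50. The tests are practically the same, and the proportional-odds model is ordinary logistic regression.

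**The case against.** The strongest reply is that nothing in the documents says the item is graded. Classing it as categorical with a logistic model fits a yes/no or likely/unlikely question perfectly well, and then nothing is lost. This stands, and it is why the point is conditional. It does not remove the point, because the proposed methods give essentially the planned analysis on a binary item.

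A second reply is that logistic regression may already mean ordinal logistic regression. That also stands: a reader might infer that the planned model forces a two-level collapse, but the text does not say so. Only the chi-square step firmly ignores order. The model's form is simply unstated.

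Third, the stated aim is the effect on decisional capacity. No power is claimed for the likelihood item, and the 0.75 shift is not a documented expectation for it. This limits the weight of the point and is why the loss is given as a range.

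A reader might go further and infer that the data types are reversed, with preferences wrongly modelled as continuous because "who they think should make the decision about enrolling in a trial" sounds like a choice among parties. The documents do not support this. That phrase is an example of pre-test content. The listed outcome is a preferred level of involvement, which suggests an ordered item for which a mean and a linear model can be reasonable. The response options are not given, so no error in the preferences analysis can be shown.

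**Conclusion.** The point holds conditionally. The plan assigns the likelihood item to a test that ignores order, names no order-respecting alternative, and leaves the logistic model's form and cut-point open. With three or more levels, power is lost. Under a 0.75 SD latent shift, 3 to 5 levels and two-sided 0.05, a rank test has about 77-82% power at 35 per arm, where the chi-square has 54-67% and a mid-scale split 59-69%. At 25 per arm the figures are about 62-68% against 35-52% and 47-61%.

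A single figure, such as a loss of one fifth, is not supported, because the size depends on the number of levels, the effect and the sample size. For a yes/no item the loss is zero. The direction is secure for an ordered item whose responses shift as a whole. The matter is secondary to the decisional capacity analysis, but it should be settled before data are analysed.

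**What to change.** In Statistical Methods, for likelihood of participating:

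- State the response options and their coding.
- Replace the chi-square with a Wilcoxon/Mann-Whitney test.
- Specify the logistic model as proportional-odds, with the planned covariates, and report a common odds ratio for group with its confidence interval. On a two-level item this is ordinary logistic regression, so the wording is safe whatever the scale.

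Keep linear regression for preferred level of involvement, provided it is scored on one ordered scale, and say so.

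The cost is SAP wording only, with no new data or participants. The one downside is that proportional odds needs a brief check, for example by setting the odds ratios at each cut-point side by side.
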